#### **9.3.2 Overall Survival**

Overall survival (OS) is defined as the number of days from the date of registration to the date of death, irrespective of the cause. In the event of no death, overall survival will be censored at the last known alive date.

OS will be analyzed using the similar methods as RFS.

#### **9.3.3 Non-Relapse Mortality**

Non-relapse mortality (NRM) is defined as time to deaths without relapse/recurrence. Deaths from any cause without prior progression are events. Events related to the disease such as relapse and progression are competing events. Patients lost to follow-up are censored.

NRM will be analyzed using the similar methods as RFS.

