#### **9.3.1 Relapse-Free Survival**

The primary endpoint, RFS, is defined as the time from the date of registration to disease relapse after SCT, or death, whichever occurs earlier. If patients discontinued treatment due to toxicity, and withdrew consent without relapse disease (RD) or death at the time of data cut off, RFS will be censored at the date of the last assessment.

RFS will be analyzed using Kaplan-Meier methodology. Kaplan-Meier curves will be plotted. Median relapse-free survival will be estimated and their 95% confidence intervals based on Brookmeyer-Crowley methodology will be calculated.

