#### **9.3.4 Time to Progression (TTP)**

Time to progression or relapse is time to first event related to the disease, such as disease progression, disease relapse/recurrence, death from disease progression, and/or initiation of any therapy given to prevent relapse. Deaths without prior relapse/recurrence (i.e., NRM) are competing events.

TTP will be analyzed using the similar methods as RFS.

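### NRM and TTP have named competing events but are assigned the Kaplan-Meier methods of RFS, with no cumulative-incidence estimator and no time origin

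*Combined protocol and SAP*

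**What the plan says.** For NRM, Section 9.3.3 states that "Events related to the disease such as relapse and progression are competing events", adds that patients lost to follow-up are censored, and closes with "NRM will be analyzed using the similar methods as RFS". For TTP, Section 9.3.4 makes deaths without prior relapse the competing events and closes with "TTP will be analyzed using the similar methods as RFS". The synopsis entries for NRM and TTP say the same.

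Section 9.3.1 sets out the methods referred to: "RFS will be analyzed using Kaplan-Meier methodology", and "Median relapse-free survival will be estimated and their 95% confidence intervals based on Brookmeyer-Crowley methodology will be calculated".

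On the time origin, RFS "is defined as the time from the date of registration to disease relapse after SCT, or death". OS (9.3.2) and EFS (9.3.5) also start at registration. NRM "is defined as time to deaths without relapse/recurrence", and for TTP the text is "Time to progression or relapse is time to first event related to the disease". Neither gives a starting date.

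The plan uses the term cumulative incidence only in the GVHD objectives (Section 3.2 and synopsis), and Section 9.1 then summarises GVHD as number and percent.

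**The concern.** RFS counts both relapse and death as events, so its methods need no rule for a competing event and contain none. Carried over to NRM or TTP, a Kaplan-Meier analysis must put the competing event somewhere, and the usual choice is to censor it. That treats a patient who has relapsed as still able to have a non-relapse death later, and a patient who has died as still able to relapse. One minus Kaplan-Meier then equals or exceeds the proportion who actually have the event. The bias runs one way, and a larger sample does not remove it.

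The trial has no control arm, so NRM and relapse will be read against outside figures and against the plan's own design rates. Those rates are on the cumulative-incidence scale: Section 9.2 takes about 40% relapse plus about 30% NRM to reach a null RFS of 30%. A median would also be reported for NRM, an event that fewer than half of patients would ever have under the assumed split.

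The missing time origin lets two analysts differ. Registration, transplant and first dose are separate dates, and under Section 4.1 transplant and first dose can be months apart.

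**Working it through.** **Inputs (Section 9.2).** Null: relapse about 40% and NRM about 30% at 1 year, so RFS 30%. Alternative: RFS 50%. RFS exponential, accrual 24 months, follow-up 12 months, N = 31, one-sided alpha 0.10. The plan does not split the 50% failures at the alternative. I assume 4:3 relapse to NRM, as at the null (28.6% and 21.4%), and constant cause-specific hazards. Relapse stands in for TTP, which also counts progression and therapy given to prevent relapse.

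**The plan's own figure first.** With λ₀ = −ln 0.3 and λ₁ = −ln 0.5 per year, the event probability under the alternative is 1 − (e^(−λ₁) − e^(−3λ₁))/(2λ₁) = 1 − 0.375/1.386 = 0.7295. Expected events are 31 × 0.7295 = 22.6 (stated: 23). The mean null cumulative hazard is (λ₀/λ₁) × 0.7295 = 1.267, and the SD of observed minus expected is about 1.206. One-sample log-rank power is Φ[(√31 × (1.267 − 0.7295) − 1.2816 × √1.267)/1.206] = 90.1%, as stated. The design reproduces.

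**Kaplan-Meier against cumulative incidence at 12 months.** Let S be RFS at 12 months and w the share of failures due to the event of interest. Cumulative incidence is w(1 − S). One minus Kaplan-Meier, censoring the competing event, is 1 − S^w.

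| Scenario | Event | 1 − KM | Cumulative incidence | Excess (points) |
|---|---|---|---|---|
| Alternative, S = 0.5 | NRM, w = 3/7 | 1 − 0.5^(3/7) = 25.7% | 21.4% | 4.3 |
| Alternative | Relapse, w = 4/7 | 1 − 0.5^(4/7) = 32.7% | 28.6% | 4.1 |
| Null, S = 0.3 | NRM, w = 3/7 | 1 − 0.3^(3/7) = 40.3% | 30.0% | 10.3 |
| Null | Relapse, w = 4/7 | 1 − 0.3^(4/7) = 49.7% | 40.0% | 9.7 |

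At the null the two Kaplan-Meier figures add to 90%, although 70% of patients have failed. In patients out of 31, NRM would read as 8.0 instead of 6.6 at the alternative and 12.5 instead of 9.3 at the null.

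**Range over event timing.** If the event of interest all comes first, the excess is zero. If the competing event all comes first, the results are:
- Alternative: NRM 1 − 0.5/(1 − 0.2857) = 30.0%; relapse 1 − 0.5/(1 − 0.2143) = 36.4%.
- Null: NRM 1 − 0.3/(1 − 0.4) = 50.0%; relapse 1 − 0.3/(1 − 0.3) = 57.1%.

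**Other splits at the alternative, constant hazards.** Relapse 20% and NRM 30% gives NRM 1 − 0.5^0.6 = 34.0% (excess 4.0). Relapse 40% and NRM 10% gives NRM 1 − 0.5^0.2 = 12.9% (excess 2.9) and relapse 42.6% (excess 2.6).

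**Sampling check.** In 20,000 simulated 31-patient trials with constant hazards, the median NRM excess was 3.9 points at the alternative (5th to 95th percentile 1.1 to 8.9) and 9.7 at the null (3.8 to 18.9). For scale, the standard error of a 21.4% proportion with 31 patients is √(0.214 × 0.786/31) = 7.4 points.

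**Median.** The monthly NRM hazard is (ln 2/12) × 3/7 = 0.02476 at the alternative, giving a Kaplan-Meier median of ln 2/0.02476 = 28.0 months. At the null the hazard is 0.0430 and the median 16.1 months. Cumulative NRM under the 4:3 split never passes 3/7 = 42.9%, so a true median time to NRM does not exist.

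**The case against.** The strongest reply is that the text does not order the wrong estimator. Section 9.3.3 puts competing events and censoring in separate sentences, and it asks for similar methods, not identical ones. An analyst who knows transplant endpoints might use cumulative incidence unprompted. This stands as a condition: every figure above assumes that Kaplan-Meier censors the competing event. It does not remove the problem, because the only methods referred to are Kaplan-Meier and a median, and no estimator for competing risks is named for these endpoints.

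The sizes also rest on assumptions. The 4:3 split is not in the plan, and exponential RFS does not by itself imply constant cause-specific hazards. Section 2.4 cites an azacitidine cohort with 1-year NRM of 8% and RFS of 57%. Taking relapse as the remaining 35%, NRM would read 1 − 0.57^(8/43) = 9.9% and relapse 1 − 0.57^(35/43) = 36.7%, excesses of only 1.9 and 1.7 points. That cohort is not described as *TP53*-selected, so this is a sensitivity case. The excess could therefore be small.

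The plan specifies no 12-month percentage for NRM or TTP, so asking for one is partly an addition; still, any percentage read from the planned curve would carry the bias. The argument that fewer than half ever have the event applies to NRM and not to relapse, whose limit under the split is 4/7 = 57.1%. A Kaplan-Meier median for TTP that censors deaths would nevertheless be biased. Registration is the natural default origin, so that gap alone would be minor.

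Both endpoints are secondary, with no hypothesis test or decision rule attached, and the excess at the alternative is below one standard error. That limits the severity. A one-directional error that one sentence removes is still worth removing.

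**Conclusion.** The concern holds. The plan recognises the competing risks and then refers to methods that cannot use them. Followed in the ordinary way, those methods overstate 12-month NRM and relapse by about 4 points at the design alternative and about 10 at the null, given constant hazards, the 4:3 split, and censoring of the competing event. Over all event timings the NRM excess runs from 0 to 8.6 points at the alternative and from 0 to 20 at the null. For relapse the ranges are 0 to 7.8 and 0 to 17.1. This should be fixed before analysis. The primary RFS test, the sample size and the safety rules do not depend on it.

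**What to change.** In Sections 9.3.3 and 9.3.4 and in the two matching synopsis entries, replace the reference to the RFS methods with one sentence. It should say that the endpoint is estimated by cumulative incidence (Aalen-Johansen) at 12 months with a 95% CI, from the same time origin as RFS, using the competing events already named. Drop the Kaplan-Meier median for both endpoints. As a wording clarification only, state in the TTP definition that study treatment does not count as therapy given to prevent relapse, since maintenance treatment could be read that way.

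The cost is one sentence in each of four places. Standard software does the analysis, no new data are needed, and the sample size does not change.

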#### **9.3.4 Time to Progression (TTP)**

Time to progression or relapse is time to first event related to the disease, such as disease progression, disease relapse/recurrence, death from disease progression, and/or initiation of any therapy given to prevent relapse. Deaths without prior relapse/recurrence (i.e., NRM) are competing events.

TTP will be analyzed using the similar methods as RFS.

#### **9.3.5 Event-Free Survival (EFS)**

EFS is defined as from registration to the first of: morphologic disease relapse, death from any cause, reappearance of a pre-transplant cytogenetic alteration, DLI for the purpose of treating MDS/AML, or institution of anti-MDS/AML therapy.

## **10.0 QUALITY CONTROL AND QUALITY ASSURANCE PROCEDURES**

### **10.1 Monitoring of the Study and Regulatory Compliance**

The project manager, or designee, will make an initiation site visit to each institution to review the protocol and its requirements with the Investigator(s), inspect the drug storage area, fully inform the Investigator of his/her responsibilities and the procedures for assuring adequate and correct documentation. During the initiation site visit the case report forms (CRFs) will be reviewed. Other pertinent study materials will also be reviewed with the Investigator's research staff. During the course of the study, the monitor will make regular site visits in order to review protocol compliance, examine CRFs and individual subject's medical records and assure that the study is being conducted according to pertinent regulatory requirements. All CRF entries will be verified with source documentation. The review of medical records will be done in a manner to assure that patient confidentiality is maintained.

### **10.2 Curricula Vitae and Financial Disclosure of Investigators**

All Principal Investigators will be required to provide a current signed and dated curriculum vitae, a completed FDA Form 1572 and a financial disclosure statement to [REDACTED]. All Sub-investigators will be required to provide a current curriculum vitae and a financial disclosure statement to [REDACTED].

### **10.3 Protocol Modifications**

No modification of the protocol should be implemented without the prior written approval of the Sponsor or the Sponsor's representative [REDACTED]. Any such changes which may affect a patient's treatment or informed consent, especially those increasing potential risks, must receive prior approval by the IRB/IEC. The exception to this is where modifications are necessary to eliminate an immediate hazard to trial subjects, or when the change involves only logistical or administrative aspects of the trial (e.g., change in monitor, change in telephone number). Other administrative revisions which may impact the clinical portion of a study will be duly reported to the IRB/IEC by the Principal Investigator.

### **10.4 Publication Policy**

The Investigator agrees to inform the Sponsor of any publication or presentations on the study. All manuscripts, abstracts or presentations (in outline form with copies of

slides if available) will be submitted to the Sponsor and [REDACTED] x at least 30 days prior to the submission of the data for publication in order for the Sponsor to protect proprietary information. The Sponsor will review the submitted material within a reasonable period of time and will not unreasonably withhold publication permission.

## **11.0 ETHICAL CONSIDERATIONS**

### **11.1 Informed Consent**

The Investigator will obtain written informed consent from each patient, or their authorized representative, participating in the study. The form must be signed, witnessed and dated. The informed consent form will contain all the Essential Elements of Informed Consent set forth in 21 CFR, Part 50, the European Union Directive 2001/20/EC and its associated Detailed Guidances, European Union GCP Directive 2005/28/EC, the ICH Guideline for Good Clinical Practice, Section 4.8, and the terms of the Declaration of Helsinki (2013). Copies of the signed document should be given to the patient and filed in the Investigator's study file, as well as the patient's medical record if in conformance with the institution's Standard Operating Procedures.

In cases where minors or incapacitated subjects are to be included, two sets of information sheets might be needed according to national regulations. In addition to the information given to the patient's parent or legal representative, the patient should be given information according to his/her capacity to understand. This information should include, where appropriate, a statement that the patient's decision not to participate or to withdraw from a trial will be respected, even if consent is given by the parent/legal representative.

### **11.2 Institutional Review Board/Independent Ethics Committee**

The study will not be initiated without approval of the appropriate Institutional Review Board/Independent Ethics Committee (IRB/IEC) and compliance with all administrative requirements of the governing body of the institution. This protocol, consent procedures, and any amendments must be approved by the IRB/IEC in compliance with current regulations of the FDA and the European Union as applicable and in accordance with ICH/GCPs. A letter of approval will be sent to the Sponsor prior to initiation of the study and when any subsequent modifications are made. The IRB/IEC will be kept informed by the Investigator, [REDACTED] or the Sponsor, as required by national regulations, as to the progress of the study as well as to any serious and unexpected adverse events.

### **11.3 Patient Privacy**

In order to maintain patient confidentiality, all case report forms, study reports and communications relating to the study will identify patients by initials and assigned

patient numbers; patients should not be identified by name. In accordance with local, national or federal regulations, the Investigator will allow the Sponsor or designee personnel access to all pertinent medical records in order to verify the data gathered on the case report forms and to audit the data collection process. Regulatory agencies such as the US Food and Drug Administration (FDA) and the UK Medicine and Healthcare Products Regulatory Agency (MHRA) may also request access to all study records, including source documentation for inspection. Clinical information will not be released without the written permission of the patient as outlined in the patient consent form.

## **12.0 DATA HANDLING AND RECORD KEEPING**

### **12.1 Recording of Data**

Data collected during the study will be entered in the patient's Case Report Form (CRF) by the investigational site staff. The staff will keep records of the patient's visit in the files considered as source documents for the site, e.g., hospital chart, research chart. The Investigator will be responsible for the recording of all data on the CRF and for submitting the data to the Sponsor or their designee in a timely manner. Should any value be significantly different from normal, the Investigator will comment in the appropriate sections provided in the CRF.

The Investigator will provide access to his/her original records to permit a representative from the Sponsor to verify the proper transcription of data. To facilitate photocopying, entries must be recorded legibly in black ink only. Erroneous entries will be crossed out with a single line, so as to remain legible. The correct value will be entered above the error and then initialed and dated by the person authorized to make the correction.

### **12.2 Study Records**

U.S. Federal laws require that an Investigator maintain all study records for the indication under investigation for two years following the date a Product Licensing Application is approved or, if no application is to be filed or if the application is not approved for such indication, until two years after the investigation is discontinued and the FDA is notified.

Subject's medical files should be retained in accordance with applicable legislation and in accordance with the maximum period of time permitted by the hospital, institution or private practice.

## APPENDIX A- KARNOFSKY PERFORMANCE SCALE

Condition	Performance status %	Comments
Able to carry on normal activity and to work. No special care needed.	100	Normal. No complaints. No evidence of disease.
	90	Able to carry on normal activity. Minor signs or symptoms of disease.
	80	Normal activity with effort. Some signs or symptoms of disease.
Unable to work. Able to live at home and care for most personal needs. A varying degree of assistance is needed.	70	Cares for self. Unable to carry on normal activity or to do active work.
	60	Requires occasional assistance, but is able to care for most of personal needs.
	50	Requires considerable assistance and frequent medical care.
Unable to care for self. Requires equivalent of institutional or hospital care. Disease may be progressing rapidly.	40	Disabled. Requires special care and assistance.
	30	Severely disabled. Hospital admission is indicated although death is not imminent.
	20	Hospitalization necessary. Very sick, active supportive treatment necessary.
	10	Moribund; fatal processes progressing rapidly.
	0	Dead.

## APPENDIX B- SCHEDULE OF EVENTS

**Table 10: Pre-Screen, APR-246/azacitidine Screening, Cycles 1-4 (Treatment Period)**

	Pre-screen	HSCT	Post HSCT/Screening Period APR-246/AZA (3)	APR-246/AZA Treatment Cycle 1						APR-246/AZA Treatment Cycles 2, 3, 4 (Cycles 5+; see Table 11)				
Day	-28 to -1 to HSCT	0	Max up to Day 100 post-HSCT	1 (first dose)	2, 3, 4	5	7, 14, 21	28	1 (D29 prior cycle)	2, 3, 4	5	14	28	
Window				NMT 28 days after engraftment confirmation			+/ -3	+/ -3 *	+28			+/ -3	+/ -3 *	
Informed Consent	X		X											
HSCT-eligibility	X													
TP53 mutation confirmation	X													
Engraftment confirmation			X (3)											
APR-246				X	X				X	X				
Azacitidine				X	X	X			X	X	X			
APR-246/AZA Eligibility			X (4)											
Karnofsky Performance Status			X											
Medical History and Transplant Details			X (4)											
Physical Exam with Weight			X (5)						X	X (5)			X	
Vital Signs			X (5)					X	X	X (5)			X	
CBC			X (5)					X	X	X (5)			X	
CMP			X (5)					X	X	X (5)			X	
Cardiac function (ECG)	X		X (5) (7)	X (7)	X (7)				X (7)	X (7)				
Pregnancy Test (1)	X		X (5)											
Disease Assessment (9)	X		X (4)					X (9)					X (9)	
BM/BMA for Correlatives/exploratory (2)	X (2)		X (2)										X (2)	
GVHD monitoring			X					X					X	
Blood sample (chimerism)													Cycle 3 (8)	
Blood sample for flow (immune reconstitution)			X (4)											
PK sampling (blood)				X (6)	X (6)									

	Pre-screen	HSCT	Post HSCT/Screening Period APR-246/AZA (3)	APR-246/AZA Treatment Cycle 1						APR-246/AZA Treatment Cycles 2, 3, 4 (Cycles 5+; see Table 11)				
Day	-28 to -1 to HSCT	0	Max up to Day 100 post-HSCT	1 (first dose)	2, 3, 4	5	7, 14, 21	28	1 (D29 prior cycle)	2, 3, 4	5	14	28	
Window				NMT 28 days after engraftment confirmation			+/- 3 *	+/- 3 *	+28			+/- 3	+/- 3 *	
Adverse Events			X	X	X	X	X	X	X	X	X	X	X	
Concomitant Medications			X	X	X	X	X	X	X	X	X	X	X	

(1) Pregnancy test applies to women of child-bearing potential only.

(2) Bone marrow aspirate sample and biopsy core are collected for correlatives/exploratory (per Section 8.5) when bone marrow is sampled for disease assessment.

(3) APR-246/azacitidine Screening Period starts when engraftment is confirmed between Day 30 to 100 post-HSCT. The first dose must be administered no more than 28 days after engraftment is confirmed.

(4) Perform within 28 days prior to first dose (Cycle 1 Day 1).

(5) Perform within 3 days prior to first dose (Cycle 1 Day 1); for Cycle 2+, do not need to repeat if done within 3 days prior to dosing.

(6) PK: see Section 8.4.

(7) Day 1 ECGs for all patients; see Table 7. Day 2, 3, 4 Additional ECG monitoring in select patients; see Section 6.2.

(8) CD3/CD33 in the blood should be done every 3 months same time marrows for disease assessment are being done. Additionally, whole bone marrow chimerism should be done from the marrow every 3 months collected at same time disease assessment labs are done

(9) Disease assessment by blood test must be done after every cycle. Response assessment based on CBC may utilize the most recently available bone marrow results. Disease assessment by bone marrow is done C3.

\* Up to 14 day window is permitted for disease assessments.

**Table 11: Cycle 5-12 (Treatment Period), EOT, 30 day Safety FUV, LTFU**

Day	APR-246/AZA Treatment Cycles 5 - 12					EOT (5)	Follow-up safety visit	Long Term Follow-up (6)
	1 (D29 prior cycle)	2, 3, 4	5	14	28			
Window	+28			+/- 3	+/- 3 *			
APR-246	X	X						
Azacitidine	X	X	X					
Physical Exam with Weight	X (3)				X			
Vital Signs	X (3)				X	X		
CBC	X (3)				X	X		
CMP	X (3)			X	X	X		
Cardiac function (ECG)	X (4)	X (4)				X		
Pregnancy Test (1)						X		
Disease Assessment					X (8)	X	X (6)	
BM/BMA for Correlatives/exploratory (2)					C 6, 9, 12 (2)			
GVHD monitoring					X		X (6)	
Blood sample (chimerism) (7)					C 6, 9, 12			
Blood sample for flow (immune reconstitution)					C 5, 11			
Adverse Events	X	X	X	X	X	X	X	
Concomitant Medications	X	X	X	X	X	X	X	
Survival								every 6 months

(1) Pregnancy test applies to women of child-bearing potential only.

(2) Bone marrow aspirate sample and biopsy core are collected for correlatives/exploratory (per Section 8.5) when bone marrow is sampled for disease assessment.

(3) Do not need to repeat if done within 3 days prior to dosing.

(4) After Cycle 4, perform additional ECG monitoring in select patients; see Section 6.2.

(5) EOT: see Section 7.3.

(6) LTFU applies to all patients. LTFU via phone call for survival will occur every 6 months until death or study closure. If GVHD or response assessment is conducted by the site per institutional standard of care, the site should report results to the sponsor until relapse is documented.

(7) CD3/CD33 in the blood should be done every 3 months same time marrows for disease assessment are being done. Additionally, whole bone marrow chimerism should be done from the marrow every 3 months collected at same time disease assessment labs are done

(8) Disease assessment by blood test must be done after every cycle. Response assessment based on CBC may utilize the most recently

available bone marrow results. Disease assessment by bone marrow is done C3.

\* Up to 14 day window is permitted for disease assessments.

